SQ53 is a novel antimicrobial, sporicidal aqueous solution that is based on a platform of quaternary ammonium chloride compounds. Other active components include polymeric biguanide, chlorocresol, bronopol and ethanol. It has been tested against a wide range of bacteria, viruses, spores and fungal pathogens. Extensive laboratory testing has demonstrated the effectiveness of SQ53 impregnated wipes in cleaning surfaces including catheters over a 24 hour plus time period. In addition, it includes no development of VNBC (Viable-but non culturable bacterial colonies) populations or evidence of resistance to the active compounds. SQ53 also received an in vitro evaluation of the irritancy potential using a tissue engineered human skin model and was found to have no potential for skin irritation. In Europe, SQ53 currently has a class 1 CE mark and is cleared and registered under European Union Biocidal Product Regulations in UK, Germany, France, Belgium and Austria. SQ53 is available as a single wipe per pack which is prepared in biocide driven sterilized environment. The pack is easy to open by tearing off the top end and presenting the contents to the operator to remove under sterile conditions.

SQ53 has been studied in India in 148 patients in two groups. Group 1 had the patients who required long term CVC for PN (n = 42, 31 adults and 11 pediatric patients) and dialysis (n=106). Group 2 had the patients who required PN for short duration for postop complications (n=14). The study findings (which are in the publication process) support a substantial improvement in the CRBSI rates **from 131 episodes per 1000 (48 per 365 days) days to 9 episodes per 1000 (3 episodes per 365 days) resulting in an overall 94% reduction**. None of the enrolled patient's experienced local or systemic adverse effect with the use of SQ53 wipes.

[figure not shown]
Study significance:

1. Ethanol Lock Therapy (ELT) which is currently used for prevention of CRBSI is an off-label usage of a commercially available product that will no longer be readily available for patients receiving home parenteral nutrition. Another breakthrough use of ELT has precluded the possibility of ELT use for PN patients. It is critical to identify and explore other agents and alternate therapeutic

approaches to prevent excess morbidity and mortality resulting from preventable CRBSI. SQ53 has shown promising results in CRBSI prevention trial conducted outside the United States.

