 - 2. Immunocompromised state increasing the infection risk
 - a. Clinical determination based on comorbidities such as HIV, immunosuppressant medications, and steroids (prednisone >40mg per day)
 - 3. History of multiple catheter exchange in the past (greater or equal to 2 within the past 6 months) with difficult access
 - a. This determination to be made based on patient's history
 - ii. Identification of Low risk patients:
 - 1. Patients who do not meet High-risk criteria will be classified as Low risk patients
 - iii. New patients:
 - 1. New patients are the patients who are newly started on PN during their in-patient stay and those who have been on PN less than 6 months unless they had CRBSI in the time frame.
 - 2. These patients will receive information about the clinical trial by RNs who provide education as standard of care.
- d. Patients can also be enrolled in the study at the time of outpatient visit, or before discharge from the hospital.
- 3. Cleveland Clinic Home Infusion Pharmacy (CCHIP) will be informed about patient's enrollment and the risk category (High vs Low vs New patient) and the catheter type (PICC or tunneled)
 - a. CCHIP will perform stratified randomization and assign the patient to either Treatment (SQ53) or PLACEBO (Alcohol wipes) group.
- 4. Treatment group will also have the SQ53 impregnated wipe used on a remote site to check for hypersensitivity and any other skin reactions before it is deemed safe to use routinely in that patient.

5. All enrolled patient will need to agree to reach out to Home Nutrition Pager which is available 24x7 in case of noted adverse effect – this is standard of care for home PN patients.

Exclusion criteria:

1. Age less than 18 years
2. Women known to be pregnant (patient will be asked verbally- no pregnancy test will be performed)
3. Women of childbearing age who are planning a pregnancy
4. Women who are breastfeeding
5. Patient's refusal to enroll in the study at any point in time
6. Patients who refuse to use disinfectant wipes daily.
7. Patients who use port for their PN infusion.
8. Patients who are enrolled in other clinical trials with investigational drugs or device

Blinding and Randomization:

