3. Patients whose compliance is less than 90 percent will be excluded from Per Protocol analysis; however, those patients will be accounted in intention to treat analysis. Patients who developed skin reaction in remote site (e.g., forearm) will be excluded from Per Protocol analysis, but will be included in intention to treat analysis
 - a. Compliance will be determined by HPN dietitian at the time of phone/virtual visit encounters: patient will be asked about their disinfectant wipe use and compliance.
4. Our primary outcome measure (as listed in above data sheet) will be differences in the CRBSI rate at 6 months after patient enrollments into the trial (i.e. SQ53 use). We will also perform sub-analysis by utilizing patients as their own controls. Please see the detailed timeline below.
5. We will also analyze the differences in the number of admissions for CRBSI (which would include admission with suspect CRBSI), as well as, overall number of catheters changed for confirmed and suspected CRBSI.
6. We will perform Poisson Regression analysis to compare the rates and 95 % confidence interval of the differences in CRBSI rates and CRBSI admissions.
7. We will also perform a descriptive analysis identifying the most common microorganisms causing the CRBSI in the periods both before and during the SQ53 therapy.
8. We will also perform a survival analysis to plot a Kaplan-Meier curve

9. We will collect mortality data of patients. We will report an overall mortality, as well as, CRBSI-specific mortality in patients using SQ53 for CRBSI prevention.

Sample size and power calculation:

1. In the un-published study conducted in India SQ53 has been reported to reduce the CRBSI rate by 94%. We expect this effect size to be lower in our cohort. We performed our sample size calculation by utilizing the data reported in our previous study which reported CRBSI rates in high risk PN patients (Pre-ELT CRBSI rate= 3.53 and post-ELT 1.65 per 1,000 catheter days). Considering current CRBSI rate in our high-risk population to be 1.65 per 1000 catheter days, we will need a sample size of 46 patients to identify a 50% reduction in CRBSI rate with alpha of 0.05 and 80 % power.

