2. To account for the patient attrition due to mortality, lost follow up and non-compliance (for per-protocol analysis), we would like to increase our sample size by 30% to this estimated calculation and would need to enroll 30 patients in each group of our study to make determinations of differences with statistical significance.

Safety concerns: Risk to the study participants: Minimal

1. Our study is a single blinded randomized placebo-controlled phase III clinical trial which utilizes disinfectant wipes which are meant for external use only. These wipes have proven to be safe in the in-vivo and in-vitro studies.
2. No major adverse effect has been reported in previous clinical trial.
3. Current data suggest that SQ53 has no potential for skin irritation; however, if a patient experiences hypersensitivity skin reaction to any of the ingredients in the formula, then those patients will be excluded from the study and use of wipes will be discontinued.
4. Collected PHI data will be securely protected on the Cleveland Clinic Network drive.

Timeline:

Please see below a simplified timeline for this project.

Time Period	Activity
-------------	----------

	
Project Lead: [name]
 
Project mentors: [name] and [name]
 
Project team members: [name], [name], [name] and [name], [name], [name]

June 2020 - Sept 2020	
 1. Protocol and team development 2. Investigational New Drug (IND exemption process) 3. FDA exemption given by CCF IDE office considering the wipes as low risk device 
Personnel responsibility:
 
Above steps have been completed

Oct 2020 – Nov 2020	
 1. Protocol submission to CHN & budget acquisition 2. Protocol submission to DDSI 3. Protocol submission to IRB 
Personnel responsibility:
 
Above steps have been completed.
 
 - Protocol for IRB/CHN/DSFI submission is ready - Cover letter is ready - Informed consent document is ready - Budget is done

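### Known hypersensitivity to a study-wipe component is not screened for before randomisation, leaving an avoidable remote-site exposure and a one-arm per-protocol loss possible (minor)

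*Combined protocol and SAP*

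**What the plan says.** - **Ingredients.** The Introduction describes SQ53 as based on quaternary ammonium compounds and adds: "Other active components include polymeric biguanide, chlorocresol, bronopol and ethanol".
- **Eligibility.** The Exclusion criteria have eight items: age, pregnancy, planned pregnancy, breastfeeding, refusal to enrol, refusal of daily wipes, use of a port and, last, "Patients who are enrolled in other clinical trials with investigational drugs or device". None concerns allergy, and the inclusion text has no allergy question.
- **Order of steps.** Under Inclusion criteria and patient recruitment, item 3a reads "CCHIP will perform stratified randomization and assign the patient to either Treatment (SQ53) or PLACEBO (Alcohol wipes) group". Item 4 follows: "Treatment group will also have the SQ53 impregnated wipe used on a remote site to check for hypersensitivity" and other skin reactions, "before it is deemed safe to use routinely in that patient". The alcohol-wipe arm has no matching step.
- **Skin contact.** Under Intervention, patients in both arms use the wipe on the exit site and surrounding skin at each dressing change.
- **Handling of reactors.** Item 3 of the data analysis section says that patients who react at the remote site "will be excluded from Per Protocol analysis, but will be included in intention to treat analysis". Safety concerns item 3 says that "if a patient experiences hypersensitivity skin reaction to any of the ingredients in the formula, then those patients will be excluded from the study", and that the wipes are discontinued.

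**The concern.** The protocol names the main actives and foresees hypersensitivity reactions to them, but it does not ask patients about allergies they already know of. As the criteria stand, a patient who reports such an allergy when consent is taken is still eligible.

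Two things are at stake. The first is an exposure that a history question could have avoided. The second is comparability of the per-protocol sets: remote-site reactors are dropped from the SQ53 set, while similar patients allocated to alcohol wipes have no such test and are not dropped on that ground.

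**Working it through.** The plan gives no allergy prevalence or expected reaction rate, so there is no figure of its own to reproduce on this point. The check is a reading of the sequence, followed by a sizing under stated assumptions.

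**Sequence for a patient with a known allergy to an SQ53 ingredient**
1. Consent: no allergy question is specified, and no exclusion item applies.
2. Randomisation by the pharmacy, 1:1.
3. If allocated to SQ53: remote-site application, which is the first exposure. If allocated to alcohol wipes: no test.
4. If the patient reacts: out of per-protocol but in intention-to-treat (data analysis section, item 3), or out of the study with wipes discontinued (Safety concerns, item 3). Neither text says whether follow-up for CRBSI continues, so the two must be reconciled.

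**Inputs for the sizing**
- Arm size 30 (Sample size and power calculation, item 2): 46 × 1.3 = 59.8, rounded to 60, so 30 per arm.
- Control rate 1.65 per 1,000 catheter days and a 50% reduction, so 0.825 (same section, item 1).
- Follow-up of 6 months, taken as 182.5 days.
- Alpha 0.05, taken as two-sided because the plan does not say.
- Assumed share h of SQ53 patients who react at the remote site: 1% to 10%. This range is illustrative and does not come from the documents.

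**Formulas**
- Expected per-protocol loss = 30 × h.
- Probability of at least one loss = 1 − (1 − h)^30.
- Power = Φ( ln 2 / √(1/E1 + 1/E2) − 1.96 ), where E1 = 30 × 1.65 × 0.1825 = 9.03 control events and E2 = 30(1 − h) × 0.825 × 0.1825 SQ53 events.

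With no loss, E2 = 4.52: 0.693 / √(0.1107 + 0.2214) = 1.203, and Φ(1.203 − 1.96) = 22.4%. With h = 10%, E2 = 4.07: 0.693 / √(0.1107 + 0.2460) = 1.161, and Φ(1.161 − 1.96) = 21.2%.

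| Assumed h | Expected loss of 30 | P(at least one) | Power |
|---|---|---|---|
| 0 | 0 | 0 | 22.4% |
| 1% | 0.3 | 26% | 22.3% |
| 2% | 0.6 | 46% | 22.2% |
| 5% | 1.5 | 79% | 21.8% |
| 10% | 3.0 | 96% | 21.2% |

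The low starting power is a separate sample-size matter. What counts here is the change down the last column, at most 1.2 points. Patients with an allergy already known are only part of h.

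**The case against.** Several points on the other side stand.

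- **The remote-site test is a real safeguard.** It applies to every SQ53 patient before routine use, and a 24-hour pager is available for adverse effects. It limits the exposure but does not avoid it, because it works by applying the product.
- **Safety concerns item 3 is about reactions on study.** A reader might infer that the plan already treats known allergy as disqualifying and merely applies the rule too late. The text covers a reaction that a patient experiences, not a condition at baseline.
- **No such patient is reported.** The criteria leave the possibility open and no more. The earlier study reports no local or systemic adverse effect. With 148 patients the one-sided 95% upper bound is 1 − 0.05^(1/148) = 2.0%; if its stated subgroups are added (42 + 106 + 14 = 162), it is 1.8%. That study is unpublished and its allergy screening is unknown, so this does not bound the share with a known allergy here.
- **The arm contrast is limited.** It is firm for the remote-site test. A reader might infer that all allergy-related loss falls on SQ53, but SQ53 contains ethanol, the comparator is an alcohol wipe, and both arms use ethanol caps. An alcohol reaction could arise in either arm, and compliance below 90% removes patients from per-protocol in both.
- **Dilution of the intention-to-treat estimate is not shown.** A reader might infer it, but its size depends on a prevalence that the documents do not give, and on every such patient consenting, reacting and gaining nothing.
- **The remedy is partial.** Patients with unknown sensitivities would still leave per-protocol from the SQ53 arm only.

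The consent form is not available here, so any allergy wording in it cannot be judged.

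**Conclusion.** The omission is real and minor. The exclusion list does not cover known hypersensitivity to a component of either wipe, and the only check comes after allocation, in one arm, by exposure. Followed as written, the plan allows a foreseeable exposure at the test site and a per-protocol loss from the SQ53 arm through that test. Intention-to-treat membership is kept under the data analysis section; whether the patient remains in the study is unclear until that section and Safety concerns item 3 agree.

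Under the assumed 1% to 10%, the loss is 0.3 to 3 of 30 patients, with little effect on power. The documents support neither a claim of material bias in the intention-to-treat result nor a claim that allergic patients have in fact been enrolled. The case for change rests on avoidable exposure and, secondarily, on the known-allergy part of the one-arm per-protocol loss.

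**What to change.** - Add an exclusion criterion for known hypersensitivity to any component of either study wipe. Ascertain it by history when consent is taken, whether by phone, at an outpatient visit or before discharge. Do this before the pharmacy randomises and identically for both arms. Pregnancy is already ascertained by asking, so the method fits existing practice.
- Ask against the full ingredient list of both wipes. The Introduction's list of actives is not stated to be exhaustive, and the type of alcohol in the comparator is not given. Define what counts as hypersensitivity to alcohol.
- Keep the remote-site test for sensitivities that patients do not know of.
- Reconcile item 3 of the data analysis section with Safety concerns item 3 on whether a reactor stays in the study and is followed for CRBSI.

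The cost is one eligibility line, one question at an existing contact, and a few patients made ineligible. The one-arm loss from unknown sensitivities remains.

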Nov 2020 – Dec 2020	
 1. Once IRB is approved: send letters to patients 2. Obtain informed consent and enroll patients 3. Risk category assessment 4. Baseline data collection 5. Randomization 6. Shipment of SQ53 or Placebo supply 
Personnel responsibility:
 
 1. Sending letters to patients: 
 - Letter has been drafted and ready, to be printed and mailed to the patients by study coordinator

	
2. Obtain informed consent
 
 - HPN dietitian 
3. Risk category assessment
 
 - HPN dietitian & NST staff 
4. Baseline data collection
 
 - HPN team, Nutrition Fellows, Study coordinator 
5. Randomization
 
 - DDSI statistician / CC Home infusion Pharmacy 
6. Supplying SQ53 and placebo wipes
 
 - CC Home infusion pharmacy
Dec 2020 to June 2021	
1. Continuation and monitoring phase of the study
 
2. Answer patient's concerns and collect data regarding specific side effects (if any)
 
3. Continue standard routine follow up: i.e. with labs, or during phone encounters
 
Personnel responsibility:
 
 - HPN dietitian, NST staff and Nutrition fellows
June 2021	
1. Perform interim analysis of the data
 
Personnel responsibility:
 
 - DDSI statistician
July 2021 to Dec 2021	
1. Continue the study for another 6 months and continue to enroll the patients
 
Personnel responsibility:
 
 - HPN dietitian, NST staff and Nutrition fellows
Jan 2022	
1. Final Analysis of the data
 
2. Reporting of the study findings
 
Personnel responsibility:
 
 - Statistical analysis: DDSI statistician

	- Reporting: All investigators
--	--------------------------------

References:

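### The timeline enrols through December 2021 and analyses in January 2022, so late enrollees cannot complete the 6-month primary window, and no data cut, exposure term or censoring rule is written

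*Combined protocol and SAP*

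**What the plan says.** - **Outcome.** Data protection, processing and analysis, item 4, defines the primary outcome as "differences in the CRBSI rate at 6 months after patient enrollments into the trial". It ties this to the data sheet and refers the reader onward: "Please see the detailed timeline below". It adds: "We will also perform sub-analysis by utilizing patients as their own controls".
- **Timeline.** The July to December 2021 row reads "Continue the study for another 6 months and continue to enroll the patients". The January 2022 row reads "Final Analysis of the data". No last-enrolment date, data-cut date or minimum follow-up is given.
- **Data sheet.** Under Data collection, the sample sheet has a Pre and a Post row for each patient in both arms. Its columns are counts over 6 months, with none for catheter-days or follow-up dates.
- **Analysis.** Item 6: "We will perform Poisson Regression analysis to compare the rates and 95 % confidence interval of the differences in CRBSI rates". Item 8: "We will also perform a survival analysis to plot a Kaplan-Meier curve". Neither states an exposure term, a time origin or a censoring rule.
- **Units.** Catheter-days appear as a rate unit in the Introduction and in the sample size section ("post-ELT 1.65 per 1,000 catheter days"), but not in the analysis items.

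**The concern.** The outcome needs 6 months of follow-up from each enrolment, and the schedule it points to does not allow that for patients enrolled in most of the second half of 2021. The plan does not say whether such patients are dropped, counted as if complete, or analysed on the time they have. Two analysts could follow the text and report different primary results.

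The risk is greatest if the sheet is analysed as drawn. A count from a shortened Post period would then be treated as a 6-month count. The primary outcome and its confidence interval are written as differences in rates, so they would shrink toward zero. In the own-control sub-analysis, a full 6-month Pre period would be set against a shorter Post period, which looks like benefit. For new patients, whose Pre period on parenteral nutrition may itself be under 6 months, a short Pre count pulls the other way.

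**Working it through.** The plan gives no cut date to reproduce, so the check is calendar arithmetic from its own dates.

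**Inputs.** Window: 6 months from enrolment, taken as 182.5 days. Enrolment: 1 July to 31 December 2021, which is 184 dates. Cut: assumed to be 31 December 2021 or 31 January 2022, because the Timeline gives only the month of the final analysis.

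**Step 1: follow-up by enrolment date.** Follow-up = min(182.5, cut − enrolment date).

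| Enrolled (2021) | Days to 31 Dec | Days to 31 Jan |
|---|---|---|
| 1 July | complete | complete |
| 1 August | 152 | complete |
| 1 September | 121 | 152 |
| 1 October | 91 | 122 |
| 1 November | 60 | 91 |
| 1 December | 30 | 61 |
| 31 December | 0 | 31 |

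The last date that completes the window is 1 July (183 days to 31 December) or 1 August (183 days to 31 January). This step needs no enrolment pattern.

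**Step 2: effect on one late enrollee if raw counts are used.** Take enrolment on 1 October and the plan's rates: 1.65 per 1,000 catheter-days in controls and 0.825 after the planned 50% reduction.

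- 31 December cut: fraction observed 91/182.5 = 0.499. The rates read as 1.65 × 0.499 = 0.82 and 0.825 × 0.499 = 0.41. Their difference is 0.41 instead of 0.825.
- 31 January cut: fraction 122/182.5 = 0.668. The rates read as 1.10 and 0.55, with a difference of 0.55.
- The ratio is 0.50 in both cases, so it is unchanged.
- With no treatment effect and a full Pre window, Post would appear lower than Pre by 1 − 0.499 = 50% or 1 − 0.668 = 33%, in either arm.

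**Step 3: average over July to December enrollees only.** Understatement = 1 − mean follow-up/182.5. The enrolment pattern is an assumption.

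| Assumed pattern | Mean days (Dec / Jan cut) | Understatement of Post rate |
|---|---|---|
| Uniform, July–December | 91.5 / 119.7 | 50% / 34% |
| All July–September | 137.5 / 162.9 | 25% / 11% |
| All October–December | 45.5 / 76.5 | 75% / 58% |

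Under the uniform pattern, 183 of 184 dates (99%) or 152 of 184 (83%) fall short of the window.

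**Step 4: whole trial.** If a share s of patients enrols late and uniformly, and everyone else is complete, catheter-days fall by s × 0.50 or s × 0.34. The documents do not give s. At s = 0 the loss is nil; at s = 0.25 it is 12% or 9%; at s = 0.5 it is 25% or 17%.

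**The case against.** **The timeline looks stale.** It is introduced as simplified. It still describes ethics submission documents as ready, although the version date falls in the month set for the final analysis. The dates may never have governed the real data cut. This stands as a limit on what can be concluded, but the outcome definition relies on this timeline and no other cut is given.

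**Nobody may be affected.** The target is 60 patients, letters go to 10–15 patients a week, and consent, enrolment and randomisation are first scheduled for November to December 2020. All 60 could have enrolled before July 2021. A reader might infer from Step 3 that a third or a half of the primary follow-up is lost. The documents do not support that: those figures need late enrolment, an assumed pattern and raw-count analysis all at once.

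**Exposure may be implied.** The outcome is called a rate, the plan's background rates are per 1,000 catheter-days, Poisson regression commonly carries an exposure term, and a Kaplan-Meier curve needs follow-up time. The sheet is only a sample. This is the more natural reading, and it suggests that follow-up time can be obtained. But the outcome is tied to that sheet, and no instruction to record or use exposure is written.

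**Randomisation protects the comparison.** Largely true. Allocation is 1:1 in blocks within strata, so late enrolment should fall about equally on both arms. A reader might infer that truncation favours SQ53 in the randomised comparison; it does not. Control patients would show the same Pre/Post artefact, so a within-arm reading of SQ53 is what is at risk.

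**Conclusion.** The current text contradicts itself: the schedule does not give patients enrolled after about 1 July or 1 August 2021 the 6-month window that the primary outcome requires. That conclusion rests only on the stated dates and an assumed cut of 31 December or 31 January.

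The size is conditional. For a late enrollee analysed by raw count, the absolute rate and the rate difference are understated in proportion to the missing time, by about 50% or 33% for enrolment on 1 October. With exposure modelled, the main cost is lost information. No whole-trial figure can be given, and zero is possible.

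It would also be too strong to say that an offset removes all bias. It corrects for unequal follow-up if the event rate is roughly constant over the window and the cut is non-informative. It does not address regression to the mean in the Pre/Post comparison, where patients can be classed as high risk because of a CRBSI in the previous 6 months.

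The point should be corrected because the written plan leaves the primary analysis open. The missing exposure rule matters even if nobody enrolled late, since the plan itself expects deaths and losses to follow-up.

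**What to change.** 1. Reconcile the Timeline with item 4 by setting the final data cut at 6 months after the last patient is randomised. If the dates have passed, state the actual cut and how many patients in each arm reached 6 months.
2. Add catheter-days to the data sheet for each patient, separately for the Pre and Post periods.
3. State that the Poisson models use a log catheter-day offset, for the between-arm comparison and for the own-control sub-analysis, with the within-patient pairing kept in the latter.
4. State that the Kaplan-Meier analysis censors event-free patients at the data cut, or at the end of their follow-up if earlier.
5. Note that the Pre/Post results remain open to regression to the mean, and read them beside the same contrast in the control arm.

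**Cost.** One added data item for each period, a few sentences and corrected dates. Moving the cut delays the report by up to about 6 months: a patient enrolled on 31 December 2021 completes 183 days on 2 July 2022. If the cut cannot move, items 2 to 5 need no delay, but follow-up is shorter and the offset relies on the conditions given in the verdict.
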